**Secondary Objectives (or Aim)**

The secondary objectives are to further determine if using ultrasound guidance for epidural placement:

- Decreases the number of attempts
- Increases the success rate in the first attempt
- Decreases the number of failed epidurals
- Leads to fewer complications including PDPH or paresthesias
- Improves patient satisfaction and anxiety levels

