This study is to be a prospective, randomized, controlled trial of morbidly obese parturients presenting to either West Penn Hospital or Magee Women's Hospital for delivery and desiring epidural anesthesia. Patients will be screened for participation in the study during the standard pre-anesthesia assessment that is already conducted by anesthesia staff on all patients presenting to Labor and Delivery. Screening will include an evaluation of the patient's medical history and BMI. The study will then be explained to patients who satisfy the inclusion and exclusion criteria and informed consent obtained should they choose to participate. A waiting period of 5-30 minutes will elapse between introduction of the study to the participant's consent to participate. At the time the patient is ready to receive their epidural, an opaque, sealed, numeric envelope labeled only with a study number will be opened containing the data collection sheet and randomly assigned group for that participant. These envelopes will be prepared prior to beginning the study by a healthcare provider not involved in the study. An online randomizer (Randomization.org) will be used to generate a random order for assignment to either the ultrasound guidance group (experimental group) or the palpation only group (control group) which will be revealed to the experimenters only upon opening the envelope at the time of epidural request. These envelopes will be distributed in equal numbers to each facility participating in the study at the onset of the study.

Once the patient has progressed in their labor to the point where they request placement of labor epidural analgesia, the primary investigator for that site ([name] at Magee, and [name] and West Penn) will be the one to open the envelope revealing which group the patient has been assigned to. This will occur during the same hospitalization as the screening visit and in many cases within just a matter of minutes to hours after the initial screening and consent process. This same person will then position the patient in

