Use of Ultrasound Guidance to Assist with Labor Epidural Placement in Patients with a BMI ≥ 40

NCT02984267

Date: 10/1/2016

Statistical analysis plan

The primary outcome is total time (minutes) to successful epidural catheter placement, defined as the sum of the ultrasound or palpation time, plus the epidural catheter placement time. The present study focused on the morbidly obese population ($BMI \geq 40$), of which we are unaware of any available data to guide a calculation for the primary outcome. Based on pilot data means and variances, total sample size will be calculated with 80% power to detect a six-minute difference in time-to-placement between groups with an alpha of 0.05 (two-tailed).

Distribution normality of continuous data will be examined using box plots and histograms. Non-normally distributed data will be compared using the Kruskal-Wallis H test, and continuous data compared with the Mann-Whitney U test. Normally distributed continuous variables will be compared using the independent sample Student t-test. The Fisher Exact test will be used for categorical variables. A P-value of ≤ 0.05 will be considered statistically significant.

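### Fisher's exact test is valid but conservative for the yes/no secondary outcomes; Boschloo's exact test keeps the 5% limit and gains some power, by an amount that depends on a sample size and event rates the plan does not state (low priority)

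*SAP*

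**What the plan says.** The second paragraph of the SAP assigns one test to every categorical outcome: "The Fisher Exact test will be used for categorical variables". It makes no exception for 2×2 tables. The threshold is the same throughout: "A P-value of ≤ 0.05 will be considered statistically significant". No multiplicity adjustment is described.

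The Protocol's Secondary Objectives include two plainly binary outcomes, "Increases the success rate in the first attempt" and "Decreases the number of failed epidurals", together with complications (post-dural puncture headache, paresthesias).

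The only power statement concerns total time: 80% power for a six-minute difference at two-sided 0.05. The sample size is deferred: "Based on pilot data means and variances, total sample size will be calculated". The SAP gives the reason: "we are unaware of any available data to guide a calculation for the primary outcome". No event rate, allocation ratio or power target is given for any binary outcome.

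**The concern.** In a randomised two-arm comparison the arm sizes are set by allocation, but the total number of successes is not fixed in advance. Fisher's test treats both margins as fixed. Few distinct P-values are then possible, and in small samples the rule P ≤ 0.05 rejects a true null well under 5% of the time. Part of the error allowance that the SAP sets is left unused, and power falls with it.

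First-attempt success is the secondary outcome closest to whether the skin mark was in the right place. Because the trial is to be sized on time alone, these outcomes have no planned reserve of power. A real benefit could be missed partly through the choice of test.

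**Working it through.** **Plan's own figure.** There is none to reproduce: the documents state no N, SD, event rate or power for a binary outcome.

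**Inputs from the SAP.** Two-sided 0.05, 80% power, six-minute difference (total time only); Fisher's test at P ≤ 0.05.

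**Assumed inputs.** Equal arms; SD of total time 6, 8, 10 or 12 minutes; first-attempt success 50% vs 75%; failed epidurals 10% vs 2%.

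**Step 1: bracket the sample size.** The normal approximation is n per arm = 2 × [SD × (1.960 + 0.842) / 6]². It gives 15.7, 27.9, 43.6 and 62.8 for the four SDs. The noncentral t calculation gives 17, 29, 45 and 64 per arm.

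**Step 2: why Boschloo cannot do worse than Fisher.** Boschloo's P-value is the maximum, over the common event rate, of the probability of a table whose Fisher P is no larger than the one observed. For any fixed total number of events, Fisher's P falls at or below a value p with probability at most p. Averaging over totals keeps that bound. So Boschloo's P is never larger than Fisher's, and every table Fisher rejects is also rejected.

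Example at 29 per arm: 0 vs 5 failures gives Fisher P = 2 × C(29,5)/C(58,5) = 2 × 118,755/4,582,116 = 0.0518, not significant. Boschloo's test at this size rejects all tables with Fisher P up to 0.082, so it rejects this one.

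**Step 3: true type I error.** All 2×2 tables were enumerated under two independent binomials. The maximum is taken over all common event rates.

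| n per arm | Fisher, maximum | Fisher, 10% rate | Fisher, 5% rate | Boschloo, maximum | Boschloo cut-off on Fisher P |
|---|---|---|---|---|---|
| 17 | 2.4% | 0.8% | 0.1% | 4.3% | 0.080 |
| 29 | 2.5% | 0.9% | 0.1% | 4.8% | 0.082 |
| 45 | 3.2% | 2.0% | 0.6% | 4.9% | 0.075 |
| 64 | 3.5% | 2.3% | 1.2% | 4.8% | 0.069 |

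Outside this range, for a common first-attempt success rate of 30% to 70%, Fisher's true level is 1.2% to 1.3% at 10 per arm and 3.5% to 4.0% at 100 per arm.

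**Step 4: power,** summed over the rejection regions of Step 3. Gains are rounded to whole points.

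| n per arm | First-attempt success 50% vs 75%: Fisher / Boschloo | Gain | Failed epidurals 10% vs 2%: Fisher / Boschloo | Gain |
|---|---|---|---|---|
| 17 | 21.3% / 30.4% | 9 | 1.6% / 1.6% | 0 |
| 29 | 39.0% / 49.3% | 10 | 3.8% / 9.6% | 6 |
| 45 | 62.5% / 68.6% | 6 | 15.1% / 25.5% | 10 |
| 64 | 80.2% / 83.6% | 3 | 31.2% / 42.8% | 12 |

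At 100 per arm the same two comparisons gain about 1 and 4 points.

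**Step 5: rarer events.** With failures at an assumed 5% vs 1%, power at the four sizes is 0.1%, 0.2%, 1.6% and 5.8% for Fisher, and 0.1%, 1.0%, 4.8% and 12.8% for Boschloo. The gain is under 1 point at the two smaller sizes. Even at 64 per arm neither test has useful power, because the number of events is the limit.

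**Step 6: other alternatives.** For 15 to 100 per arm the uncorrected chi-square test has a maximum true level of 5.3% to 6.5%, and Fisher's mid-P reached 5.7%. Part of their extra power comes from exceeding 5%, so they are not like-for-like replacements.

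**The case against.** The strongest reply is that nothing is broken. Fisher's test is prespecified, widely understood, and keeps type I error at or below 5% at any sample size and with sparse cells. The outcomes are secondary, no power target is set for them, and so no stated goal is missed. All of this stands.

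The gain is also not free. The SAP tests several secondary outcomes, each at an unadjusted 0.05, so a less conservative test on each raises the chance of at least one false positive. For two binary outcomes at 45 per arm, the upper bound on that chance goes from 2 × 3.2% = 6.4% to 2 × 4.9% = 9.8%. Each single test still respects the SAP's limit.

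A reader might infer three stronger things that the documents do not support:

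- That failed epidurals are tested at a true level of about 2% to 3.5%. Figures in that range are maxima over all event rates. If failures are uncommon the level is lower.
- That this trial loses some definite amount of power, such as ten points. The amount depends on N and event rates that appear nowhere in the documents, and it runs from nothing to about 12 points in the cases worked here.
- That Fisher's conservatism buys nothing. It does lower the actual false-positive rate across the unadjusted tests. What it lacks is any better guarantee of the 5% limit than Boschloo's test gives.

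**Conclusion.** The point holds as a low-priority efficiency improvement. Fisher's test is a valid choice here, and naming it is not an error. Under two independent binomials, Boschloo's test keeps the same 5% limit and is never less powerful. That much is general and does not depend on the assumptions.

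The size does depend on them. With equal arms of 17 to 64, which follow from an assumed SD of 6 to 12 minutes, the gain is about 3 to 10 points for first-attempt success at 50% vs 75% and 0 to 12 points for failed epidurals at 10% vs 2%. The change would not rescue comparisons of very rare complications.

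**What to change.** Replace the SAP sentence on categorical variables with:

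> Binary outcomes (first-attempt success, failed epidural, each complication) will be compared with the two-sided Boschloo unconditional exact test; Fisher's exact test is kept for tables larger than 2×2.

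State also that tables are ordered by the two-sided Fisher P-value. Two-sided versions of the test can differ when the arms are unequal, and the documents do not state the allocation ratio.

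The change should be made before outcome data are compared by arm. It needs no extra patients or data, and the test is available in SciPy and R. The costs are a test that readers know less well, and a true type I error on each unadjusted secondary test that moves toward, but not above, 5%.
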